Proportion of participants who achieve CRmin within 30 weeks as primary endpoint and treatment duration of 30 weeks: A trial duration of 30 weeks was selected based on results from the phase 2 trial ARGX-113-1701 in participants with pemphigus for encompassing the observation of the primary endpoint of CRmin in the majority of participants belonging to the active group. The time point at which CRmin is anticipated to be achieved for most participants varies between 24 and 30 weeks in participants under active treatment and depends on the body weight of the participants. Accounting for this variation between participants, all participants having achieved CRmin within the 30 weeks of the trial will be considered in the primary endpoint as responsive to treatment.

Tailored regimen of efgartigimod PH20 SC and rollover to the OLE: The trial comprises a screening period of up to 3 weeks, a treatment period until CRmin of up to 30 weeks, and an 8-week follow-up period for participants who do not enroll into the OLE trial ARGX-113-1905. A tailored efgartigimod PH20 SC regimen is proposed due to its rapid effect and the variability of disease activity between participants. Participants will be administered the efgartigimod PH20

SC with concomitant low dose prednisone regimen subcutaneously until CRmin is achieved. Then, efgartigimod PH20 SC administration will be stopped, whereas the concomitant treatment by prednisone will be pursued with the option for further tapering to achieve CR off therapy (CROff).

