4.1.2.3 OTHER SECONDARY ENDPOINTS (NOT ALPHA CONTROLLED)

All other secondary endpoints will be analyzed using the mITT population. Analyses related to data in the period after an event (CRmin, DC) can only be performed in participants with that event.

1. Proportion of PF participants who achieve CRmin within 30 weeks: same derivation as for the primary endpoint (composite strategy) but then for PF participants.
2. Time to CRmin in PV, PF and all participants: same derivation as third key secondary endpoint (composite strategy) but using date of achieving CRmin. Time to CRmin is defined as the time to the moment that the participant achieves CRmin status defined as complete remission while receiving prednisone therapy at 10 mg/day or less for at least 8 weeks, based on the assessment of the investigator. The 8-week period with minimal prednisone necessary to confirm CRmin is included as part of this time period. For example, a participant that achieves complete remission with prednisone ≤ 10 mg/day at week 15 for the first time and maintains this status for 8 weeks will have a time to CRmin of $15 + 8 = 23$ weeks.
3. Proportion of participants achieving DC in PV, PF and all participants (composite strategy)
4. Proportion of participants achieving CR in PV, PF and all participants (composite strategy)

For all subsequent secondary endpoints a treatment policy strategy is applied ignoring ICEs.

5. Proportion of treatment failures as assessed by the investigator in PV and in all participants. Specific reasons for treatment failure can be derived as follows in following order:
 - absence of DC: if participant didn't achieve DC as assessed by the investigator
 - prednisone related SAE: occurrence of an SAE after DC considered related to prednisone by the investigator
 - flare: if previous 2 reasons are not applicable, the reason must be a flare between DC and CRmin that is not controlled by a prednisone dose that is 2 dose levels above the dose at which the flare is observed and that is a least 0.3mg/kg qd

Failure is defined for the whole treatment phase.
6. Number of flares in PV and in all participants: count number of flares as assessed by the investigator. A new flare only emerges after a new DC. Number of flares are counted over the whole treatment + follow-up phase, between first DC and CRmin (or end of treatment period for participants without CRmin) and after CRmin. The initial flare at baseline (if applicable) is not counted.

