7. Time to first flare from first DC in PV and in all participants is calculated as (visit date of flare)-(date of first DC)+1. Similarly time to first flare from first CR and time to first flare from CRmin will be calculated as (visit date of flare)-(date of first CR and date of CRmin respectively)+1.

	
Statistical Analysis Plan
	

ARGX-113-1904
	
Final analysis
	
Final 2.0 of 22NOV2023

8. Proportion of PV and all participants with at least one flare after DC. The same periods are considered as for number of flares: i.e. whole treatment + follow-up phase, between first DC and CRmin (or end of treatment period for participants without CRmin) and after CRmin.
9. Duration of CRmin in PV, PF and in all participants: count the number of weeks CRmin is maintained. I.e. participant remains without a lesion after CRmin and with prednisone equivalent dose ≤ 10 mg/day maintained and with PDAI activity score=0 maintained. The 8-week period with minimal prednisone necessary to confirm CRmin is included as part of this duration. Participant is censored at EoS if still on CRmin at end of treatment phase (or follow-up phase if applicable).
10. PDAI at each visit in PV and in all participants: PDAI activity subscores (mucosal, skin and scalp), PDAI activity score and PDAI total score are assessed by the investigator at each visit. Data after the first occurrence of an intercurrent event will also be used (treatment policy strategy). Missing data (intermittent as a result of the scattered way of data collection and non-intermittent as a result of study discontinuation), will be imputed using last observation carried forward (LOCF).
11. QoL in PV and in all participants: ABQOL (17 items) and EQ-5D-5L (i.e., mobility, self-care, usual activities, pain/discomfort, anxiety/depression and VAS) are assessed by the investigator at baseline, Week 4, Week 14 and at EoS. A total ABQOL score is calculated as the sum of all 17 items score 0 to 3 with higher score indicating worse condition. Missing items are imputed with the average score of the present items if at least half (9) of the items are present. The total score is rounded to the highest integer.

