Summary statistics on NCPD, cumulative prednisone dose, number of days and proportion of days with prednisone equivalent dose ≤ 10 mg will be provided for PV participants and an ANCOVA model with factors for treatment and the stratification variables will be applied on NCPD over the whole treatment phase only. Least square (LS) means and standard error (SE) with 95% 2-sided CI for placebo and efgartigimod will be reported, along with the difference in LS means of IMP vs placebo (with SE), 95% 2-sided CI, and 2-sided p-value. A non-parametric stratified Mann-Whitney test will be performed as sensitivity for PV participants. The 2-sided p-value resulting from this hypothesis test will signify whether the null hypothesis that the distributions of the NCPD for both treatment arms are identical can be rejected. The test will be conducted at a significance level of $\alpha=0.05$. A supplementary analysis using the treatment policy strategy applying the same ANOVA model will be done.

The table with summary statistics on NCPD will be repeated by subgroups, for PF participants and overall.

Time to CR and Time to DC will be descriptively presented with median times, quantiles and number and percentage of participants censored and with event. In addition, Kaplan-Meier survival plots by treatment arm will be produced (as in-text figures only). Both treatment groups will be compared using the stratified Fleming-Harrington weighted logrank statistic FH (1,0). Also the Cox proportional hazard model will be used: the model will include treatment as fixed effects and stratification factors as covariates. The HR for efgartigimod vs. placebo will be provided, along with the associated 95% 2-sided Wald-type CI and 2-sided p-value. The table will be produced for PV participants and overall. The descriptive statistics will also be presented by subgroups.

Duration of CRmin and other 'time to event' parameters of the 'other secondary endpoints' in section 4.1.2.3 will be descriptively presented and treatment groups will be compared using the logrank statistic.

	Statistical Analysis Plan	
ARGX-113-1904	Final analysis	Final 2.0 of 22NOV2023

Frequency tabulations will be provided for the percentages of treatment failure and its different reasons. Failure rates will be compared using the same CMH-test as for the primary endpoint analysis.

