Proportion of participants achieving DC and CR and proportion of participants with flare will be tabulated and treatment groups will be compared using the same CMH-test as for the primary endpoint analysis.

Descriptive statistics for PDAI on absolute values, changes from baseline and percent changes from baseline will be calculated per timepoint. Results will be presented separately for observed data and LOCF imputed data. Changes from baseline on LOCF imputed data will be compared between treatment arms at each analysis visit using an ANCOVA model with factors for treatment, baseline value and the stratification variables. Least square (LS) means and standard error (SE) with 95% 2-sided CI for placebo and efgartigimod will be reported, along with the difference in LS means of IMP vs placebo (with SE), 95% 2-sided CI, and 2-sided p-value.

The number of flares will be descriptively presented and analyzed by the same ANCOVA model as for the NCPD analysis. Time to the first flare will be presented and analyzed in the same way as time to CR or time to DC, however using the logrank statistic.

Frequency tabulations will be provided for the percentages of participants within each outcome of QoL questionnaire items (ABQOL and EQ-5D-5L). Additionally cumulative percentages (starting with the best outcome result) will be calculated. Descriptive statistics will be provided for the total ABQOL score and for the EQ-5D-5L VAS score. Changes from baseline will be analyzed by means of a mixed model for repeated measurements (MMRM). The model will include treatment, visit and treatment by visit interaction terms as fixed effects, with baseline value, interaction of baseline value with visit, and stratification factors as covariates. Within-subject correlation will be modeled by assuming an unstructured covariance matrix (UN) for the error terms and Kenward-Roger degrees of freedom method will be used. Least square means and SE with 95% 2-sided CI for placebo and efgartigimod will be reported, along with the difference in LS means of IMP vs placebo (with SE), 95% 2-sided CI, and 2-sided p-value.

If the default Newton–Raphson algorithm used by SAS PROC MIXED fails to converge, the following will be tried to avoid lack of convergence while maintaining an unstructured variance:

- A. The Fisher scoring algorithm (via the SCORING = 5 option of the PROC MIXED statement) will be used to obtain the initial values of covariance parameters.

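### Between-arm tests of CRmin duration, time to first flare and post-CRmin flares use only participants who reached the event, so they do not compare randomised groups and should be reported descriptively

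*SAP*

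**What the plan says.** SAP 4.1.2.3, whose title marks these endpoints as not alpha controlled, starts with "All other secondary endpoints will be analyzed using the mITT population" and then narrows it: "Analyses related to data in the period after an event (CRmin, DC) can only be performed in participants with that event".

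The clocks start after randomisation. "Time to first flare from first DC in PV and in all participants is calculated as (visit date of flare)-(date of first DC)+1", and "Similarly time to first flare from first CR and time to first flare from CRmin will be calculated as" the same difference from those later dates. The restricting sentence names CRmin and DC only; CR enters through this definition. Duration of CRmin counts the weeks for which it is kept, includes the 8-week confirmation period, and is undefined for anyone who never reaches CRmin. Flare counts and flare proportions are each derived for three windows, one of which is the time after CRmin.

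SAP 4.1.3 plans tests for all of these. Duration of CRmin and the other time-to-event endpoints of that section "will be descriptively presented and treatment groups will be compared using the logrank statistic". Time to first flare is "analyzed in the same way as time to CR or time to DC, however using the logrank statistic". Flare counts go into the ANCOVA used for NCPD, and flare proportions into the CMH test used for the primary endpoint.

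The table list in SAP 8.1 labels these tables mITT and flags time to first flare as topline for PV, PF and PV+PF.

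Protocol 4.2 says of timing: "The time point at which CRmin is anticipated to be achieved for most participants varies between 24 and 30 weeks". The sentence goes on to limit this to participants on active treatment. The same section stops IMP once CRmin is reached.

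Neither document sets a principal-stratum estimand, gives a sensitivity analysis for the selection, or says that these p-values are descriptive.

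**The concern.** Randomisation protects a comparison of everyone assigned to each arm. It does not protect a comparison of those who later reach CRmin, CR or DC when treatment changes who gets there. If efgartigimod brings harder-to-treat patients into remission, its achievers are on average a more difficult group than the placebo achievers. They may then flare sooner even if the drug alters nobody's flare risk. The opposite pattern is also possible.

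At stake is how durability is read. IMP stops at CRmin, so the post-CRmin comparisons describe remission off IMP, a question that Protocol 9.3 records as arising from regulatory interactions. A topline log-rank p-value under an mITT label could be taken as randomised evidence on it.

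**Working it through.** **1. The plan's own figures.** No figure is given for these analyses. The related one is the original sample size in Protocol 9.3: 42 placebo and 84 efgartigimod, 20% versus 50%, two-sided 5%, more than 90% power.
- Pooled rate: (42 × 0.20 + 84 × 0.50)/126 = 0.40.
- Null SE: √[0.40 × 0.60 × (1/42 + 1/84)] = 0.0926. Alternative SE: √(0.16/42 + 0.25/84) = 0.0824.
- Power: Φ[(0.30 − 1.96 × 0.0926)/0.0824] = Φ(1.44) = 92.5%.
- Exact enumeration gives 92.4% (pooled z) and 90.6% (Fisher).

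The stated figure reproduces. It matters here only because it fixes the rates used below.

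**2. Size of the compared groups.** 183 PV participants at 2:1 give 122 and 61.
- CRmin achievers: 122 × 0.50 = 61 and 61 × 0.20 = 12.2.
- Over the whole planning range in Protocol Table 6 (40–50% and 1–20%): 49 to 61 on efgartigimod, 0.6 to 12 on placebo. The figure of 12 is the upper end.

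**3. How far the groups differ.** Assume that everyone who would reach CRmin on placebo would also reach it on drug. Then 20/50 = 40% of efgartigimod achievers have a placebo counterpart and 60% do not. Let r_A be the flare risk in the first kind of patient and r_D in the second, neither altered by treatment.
- Efgartigimod achievers: 0.4 r_A + 0.6 r_D. Placebo achievers: r_A.
- Spurious difference: 0.6 × (r_D − r_A).

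The documents give no values for r_A or r_D. As a range:
- gap of 0: no bias;
- gap of 10 points: 6 points against efgartigimod;
- gap of 30 points: 18 points against it (for example 10% and 40%, giving 28% versus 10%);
- gap of −10 points: 6 points in its favour.

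**4. The same effect on the log-rank scale.** In a simulation, a latent severity lowers the chance of CRmin (probit coefficient b) and raises the hazard of losing it (log-hazard coefficient g). Treatment has no effect on that hazard. The baseline hazard uses the 45% flare rate within 6 months from Protocol 2.2; b and g are assumptions.

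| Setting | Large-sample hazard ratio among achievers |
|---|---|
| CRmin 50% v 20%, severity unrelated to durability | 1.0 |
| CRmin 50% v 20%, b=1, g=0.5 | 1.22–1.23 |
| CRmin 50% v 20%, b=1, g=1 | 1.44–1.46 |
| CRmin 50% v 20%, b=2, g=1 | 1.61–1.63 |
| CRmin 20% v 20%, any of these | about 1.0 |
| Flare from DC, assumed DC 95% v 85% | 1.06–1.11 |
| Flare from DC, assumed DC 90% v 70% | 1.11–1.22 |

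The distortion appears only when the arms differ in who reaches the event and severity also affects what follows. It is smaller for DC.

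**5. Information after CRmin.** CRmin at weeks 24 to 30 leaves 0 to 6 weeks up to week 30, about 3 on average if spread evenly.
- Weekly hazard: −ln(0.55)/26 = 0.0230.
- Expected events among 73 achievers: 73 × (1 − e^(−0.0230 × 3)) = 4.9, of which 12.2 × 0.067 = 0.8 on placebo.
- Simulated: 3–5 events.
- With an assumed 4 to 14 weeks (some participants do not enter the extension and have follow-up visits): 73 × (1 − e^(−0.0230 × 9)) = 13.6; simulated 8–14.
- Simulated rejection rate at N = 183, no effect on durability: 1–5% after CRmin, 5–8% for flare from DC.

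The 8 confirmation weeks counted in duration add time but no events, because every analysed participant is event-free in them by definition.

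**The case against.** The strongest reply is that little hangs on these tests. The SAP states the restriction openly, keeps the endpoints out of the fixed sequence in 4.1.4, and lists duration of CRmin and time to first flare in 6.1 as additions to the protocol. Randomised evidence on maintained remission already exists. The week-30 landmark analysis in SAP 4.1.2.1 runs on mITT with the stratified CMH test, counts those who never reached CRmin or who lost it as non-responders, and has a sensitivity version. All of that stands and sets the limit on severity. Two qualifications remain: not alpha controlled speaks to multiplicity rather than selection, and the landmark gives status at one time rather than duration.

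It is also fair that selection on DC is likely weaker. In the phase 2 trial 24 of 31 participants reached DC within 4 weeks, and prednisone is escalated to achieve it.

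A reader might infer more than the documents support:
- **That the log-rank test is invalid as such.** If treatment affects neither reaching the event nor what follows, it is valid.
- **That false positives are inflated after CRmin.** The simulated rejection rate is 1–5%; the harm there is bias and lack of information.
- **That the bias runs against efgartigimod.** It does under the assumed severity model, but its sign in the real data is unknown.
- **That the 28% versus 10% contrast is an estimate.** It follows from chosen risks.

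**Conclusion.** The concern holds for duration of CRmin, for time to first flare from CRmin and CR, and for post-CRmin flare counts and proportions. It holds more weakly for time to first flare from DC. The p-values compare subsets chosen by an outcome that the trial is powered to change, so they are not randomised comparisons of durability.

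The group sizes rest on the protocol's planning rates. The 60% without a counterpart rests on the monotonicity assumption in step 3. The hazard ratios rest on assumed links between severity and durability and on assumed DC rates. The event counts rest on the stated CRmin timing for active participants, applied here to both arms, and on the 45% background flare rate.

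This is an optional improvement to supportive output. It does not touch the primary or key secondary conclusions.

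**What to change.** 1. In SAP 4.1.3, present these conditional endpoints descriptively and drop the between-arm p-values, at least for everything after CRmin and CR. Include the post-CRmin flare counts (ANCOVA) and proportions (CMH). If the p-value for flare from DC is kept, footnote that the groups are not randomised.
2. In SAP 8.1, label the denominators as participants who reached the event, not mITT.
3. Refer readers to the week-30 landmark analysis for randomised evidence on maintained remission.
4. Optionally, add one supportive measure in all mITT participants: days in CRmin to Day 218, 0 if never reached, compared with the stratified Mann-Whitney test already in the SAP. State that days after loss of CRmin, treatment failure, early rollover or discontinuation count as 0. Note that the measure combines reaching and keeping CRmin and is driven mainly by reaching it. An unstratified version in weeks gave 97% power at 50% versus 20% with no effect on durability built in, and 4.7% type I error at 20% versus 20%. It therefore cannot be read as evidence on maintenance alone.

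Cost: nominal p-values on supportive endpoints are lost and, if step 4 is taken, one derived variable and one table are added.

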2.2 PHASES AND TIME POINTS

2.2.1 Analysis Phases and Periods

All events and assessments will be allocated to phases and periods as defined below.

Table 1: Phase definition

Phase	Period	Start	End
Screening		Date of signing the informed consent form (ICF), with 00:00 added as time part ^a	First IMP administration date/time – 1 minute
Treatment	On Treatment	First IMP administration date/time	Last IMP administration date with 23:59 added as time part.
	Off Treatment	End of on treatment period + 1 minute	For participants who roll over to study 1905, date of study termination (of study 1904), with 23:59 added as time part. For participants who do not roll over to study 1905, date of end of study/early discontinuation visit ^b , with 23:59 added as time part. For participants who do not roll over to study 1905 and have no end of study/early discontinuation visit, date of treatment discontinuation (of study 1904), with 23:59 added as time part.
Following phase is only applicable for participants in the treatment phase who do not roll over to study 1905.			
Follow-up		End of treatment phase + 1 minute	Date of study termination (of study 1904), with 23:59 added as time part.

^a For rescreened participants without new IC signed the rescreening visit date is used as start of screening phase

^b Treatment phase lasts until EoS/ED also if a participant may be off treatment after CRmin

Per definition and for each participant, the first phase starts on the date of the earliest available ICF signature, and the last available phase ends on the date of study termination with 23:59 added as time part.

Adverse events and concomitant medications will be allocated to phases (AE's also to periods) as described in sections 5.1.2 and 3.4.2 respectively. All other assessments will be allocated to phases based on the assessment date/time.

A set of subperiods will be derived within the treatment phase, to support the analysis of treatment-emergent adverse events (TEAEs) versus post-TEAEs, as defined in Table 2 below.

Table 2: Subperiod definition for AE

Subperiod	Start	End
Treatment emergent 1	Treatment period start date/time (see Table 1)	Date of first EFG where the next EFG is at least 61 days later + 60 days ^a
Post-treatment emergent 1	End date/time of previous subperiod + 1 minute	Start date/time of next subperiod - 1 minute

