2.2.4 Analysis visits

All assessments, including unscheduled assessments, will be allocated to analysis windows as defined below. Tables and listings will present the analysis windows, not the case report form (CRF) visits. Allocation of assessments will be done using their relative day (ADYP, see section 2.2.3). Visit windows are the mid-point between the scheduled study days for each visit.

Table 3: Analysis visits

Following analysis visits are allocated based on ADYP using start of phase as reference day.

Phase	Analysis window	Target ADYP	Lower limit ADYP	Upper limit ADYP
Screening	Screening	-21	-INF	1
Treatment	Baseline	1	-INF	1 ^[1]
	Week 1	8	1 ^[1]	11
	Week 2	15	12	18
	Week 3	22	19	25
	Week (3+ x ^[2])	22 + (x ^[2] *7 days)	19 + (x ^[2] *7 days)	25 + (x ^[2] *7 days)

	Week 29	204	201	207
	Week 30	211	208	End day of treatment phase
Follow-up	FU Week 3	21	1	35
	FU Week 7	49	36	End of follow-up phase

^[1] An assessment on Day 1 will be attributed to Baseline in case it is before the first IMP administration, to Week 1 otherwise.

^[2] x=1,...,25

	Statistical Analysis Plan	
ARGX-113-1904	Final analysis	Final 2.0 of 22NOV2023

Table 4: Additional analysis visits for PD, Albumin, LDL-C and PDAI

Additionally following analysis visits are allocated based on ADYP using start of period as reference day.

Phase	Period	Analysis window	Target ADYP	Lower limit ADYP	Upper limit ADYP
Treatment	On treatment	Baseline	1	-INF	1 ^[1]
		Week 1	8	1 ^[1]	11
		Week 2	15	12	18
		Week 3	22	19	25
		Week (3+ x ^[2])	22 + (x ^[2] *7 days)	19 + (x ^[2] *7 days)	25 + (x ^[2] *7 days)
	
		Week 30	211	208	Last IMP administration date
	Off treatment	Week 1	8	1	11
		Week 2	15	12	18
		Week 3	22	19	25
		Week (3+ x ^[2])	22 + (x ^[2] *7 days)	19 + (x ^[2] *7 days)	25 + (x ^[2] *7 days)
	
		Week 30	211	208	End day of treatment phase

^[1] An assessment on Day 1 will be attributed to Baseline in case it is before the first IMP administration, to Week 1 otherwise.

^[2] x=1,...,26

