4.1.2 Endpoints and derivation rules

The analysis of primary and key secondary endpoints will be repeated on the PP set. In addition, these analyses will also be repeated on the mITT population excluding data impacted by the conflict in Ukraine, i.e. excluding participants from Ukraine that have not completed the study by the onset of conflict (24Feb2022). All the above repetitions will be performed on the primary estimand only.

For all references to weeks, analysis visits are considered as described in section 2.2.4 unless specified otherwise. If multiple assessments fall within the same analysis window, only the assessment closest to the target date will be considered unless specified otherwise. Other assessments within this window will only be listed and not considered in the below analyses. Only the time to response endpoint (see section 4.1.2.2) will be derived using all possible measurements and not only the one closest to the target of the analysis visit. Visits during the treatment and FU phase will be considered defining the different responses, unless mentioned otherwise.

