4.1.2.1 PRIMARY ENDPOINT

The primary endpoint is the proportion of PV participants having achieved CRmin (as assessed by the investigator) within 30 weeks. A stratified Cochran-Mantel-Haenszel (CMH) test will be calculated with the stratification factors of disease status, disease severity, and body weight at randomization.

Disease activity relative day will be calculated as specified in Section 2.2.3. Any CRmin achieved with a relative day up to day 218 is counted as a primary endpoint response. CRmin cases achieved for the first time after day 218 will not be considered.

The main analysis on the primary endpoint will use the ‘composite strategy’ approach in case of main intercurrent events. This strategy implies that when a main intercurrent event (ICE) occurs, a participant is considered a non-responder. This happens in the following situations:

	Statistical Analysis Plan	
ARGX-113-1904	Final analysis	Final 2.0 of 22NOV2023

- Intercurrent medications (see section 3.4.2) before CRmin
 - Immunosuppressants or dapsone at therapeutic doses for at least 4 weeks in total in the last 12 weeks before achieving CRmin
 - IVIg/SCIg at immunomodulating dose (≥ 1 g/kg/month) before achieving CRmin
 - Immunoabsorption or plasma exchange (at least 1 procedure) before achieving CRmin
 - Rituximab or other anti-CD20 biologics (at least 1 infusion) before achieving CRmin
 - IV or IM corticosteroids administered (at least 1 administration, any dose) once the participant has achieved minimal prednisone (or prednisone equivalent) dose of ≤ 10 mg/day (i.e., during the 8 week period required in the protocol to confirm the CRmin status) or administered at any moment before achieving CRmin in any of the three following situations:
 - a) more than 60 mg for 3 consecutive days
 - b) more than 40 mg for 4 consecutive days
 - c) more than 7 days in total
 - Tetracyclines administered at least 100 mg/day for at least 2 weeks in total in the last 10 weeks before achieving CRmin
 - Any interventional study drug under development for pemphigus given before achieving CRmin
- Discontinuation of IMP before CRmin due to lack of efficacy
- Death

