- Intercurrent medications (see section 3.4.2) before CR: participant is assumed to not reach CR until the theoretical end of the study and is censored at day 218.
- Discontinuation of IMP before CR due to lack of efficacy: participant is assumed to not reach CR until the theoretical end of the study and is censored at day 218.

Participants without any disease assessment are censored at day 1. Participants with disease assessment but not achieving CR in the period from Day 1 to Day 218 and without intercurrent event in that period are censored at the earliest of day 218 and the end of treatment + FU phase.

A supplementary analysis for this secondary endpoint will use the ‘treatment policy strategy’ where the occurrence of the intercurrent event is considered irrelevant: Time to CR is calculated regardless of whether or not the intercurrent event occurs.

4) Time to DC in PV participants, calculated as the difference between the first date DC was achieved and the first IMP administration date. Similar calculations, ICE handling and censoring rules are applied as for ‘time to CR’ (composite strategy).

A supplementary analysis for this secondary endpoint will use the ‘treatment policy strategy’ where the occurrence of the intercurrent event is considered irrelevant: time to DC is calculated regardless of whether or not the intercurrent event occurs.

Both time to event endpoints will be statistically evaluated using the stratified Fleming-Harrington weighted logrank statistic FH (1,0), with the stratification factors disease status, disease severity, and body weight at randomization. For both, Kaplan-Meier survival plots by treatment arm will be produced (as in-text figures only).

5) NCPD over the whole planned treatment phase in all participants: same derivation as second key secondary endpoint (composite strategy and treatment policy strategy) but for all participants.

6) Time to DC in all participants: same derivation as fourth key secondary endpoint (composite strategy) but for all participants.

7) Time to CR in all participants: same derivation as third key secondary endpoint (composite strategy) but for all participants.

	
Statistical Analysis Plan
	

ARGX-113-1904
	
Final analysis
	
Final 2.0 of 22NOV2023

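### The proportions achieving DC and CR (SAP 4.1.2.3, items 3 and 4) have no Day 218 limit, so a first response in follow-up counts, and only participants who do not roll over have follow-up visits

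*SAP*

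**What the plan says.** Items 3 and 4 of SAP 4.1.2.3 give the two endpoints as "Proportion of participants achieving DC in PV, PF and all participants (composite strategy") and "Proportion of participants achieving CR in PV, PF and all participants (composite strategy"). Neither has a time window or refers to another endpoint's derivation.

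With nothing stated, the general rule in SAP 4.1.2 governs: "Visits during the treatment and FU phase will be considered defining the different responses, unless mentioned otherwise".

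SAP 2.2.1 sets who has a follow-up phase: "Following phase is only applicable for participants in the treatment phase who do not roll over to study 1905". For rollovers the treatment phase ends at "For participants who roll over to study 1905, date of study termination (of study 1904), with 23:59 added as time part", and nothing later is recorded in this trial. The schedule of assessments (SAP 9.5) places a disease assessment at both follow-up visits, 3 and 7 weeks after EoS/ED.

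Comparable endpoints do carry a limit. For the primary endpoint, "Any CRmin achieved with a relative day up to day 218 is counted as a primary endpoint response" (SAP 4.1.2.1). For time to CR, participants with no event by Day 218 and no intercurrent event are "censored at the earliest of day 218 and the end of treatment + FU phase", and time to DC follows the same rules (SAP 4.1.2.2). The main NCPD period runs from Day 1 to Day 218 (SAP 3.5.2).

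**The concern.** How long a participant is observed for these two proportions depends on whether he or she rolls over. That is settled after randomisation and may differ between arms. A non-rollover who first reaches CR at the last follow-up visit, off IMP, is a CR responder for the randomised treatment. A rollover who reaches CR on the same day is not, because that day belongs to the extension trial.

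There is also a reporting problem. The time-to-CR and time-to-DC tables show the number and percentage of participants with an event by Day 218, while the proportion tables (14.2.1.3.2.x and 14.2.1.3.3.x) count first responses without a limit. The report could then give two different counts of CR for the same people.

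**Working it through.** **1. Is a limit stated anywhere for items 3 and 4?** Within SAP 4.1.2.3, item 1 is restricted to 30 weeks, item 2 takes over the derivation of time to CR, item 5 names the treatment phase, and items 6 and 8 name treatment plus follow-up. Items 3 and 4 give only the composite strategy. SAP 4.1.3 borrows the primary endpoint's CMH test for them, but not its Day 218 rule. Table 5 (SAP 4.1.5) adds no limit. The default in 4.1.2 therefore applies.

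**2. Visit days.** The visit in protocol week w falls on Day 7(w − 1) + 1.
- W31 (EoS): 7 × 30 + 1 = Day 211. This reproduces the SAP target for its Week 30 window (SAP 2.2.4, Table 3), whose upper limit is "End day of treatment phase".
- W34: 7 × 33 + 1 = Day 232, which is 211 + 21.
- W38: 7 × 37 + 1 = Day 260, which is 211 + 49.
- Cross-check: the last weekly dose at W30 is Day 204, and 204 + 56 = 260. The protocol's total of 3 + 30 + 8 = 41 weeks agrees.

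**3. Extra time for an on-schedule non-rollover.**
- W34 past the limit: 232 − 218 = 14 days.
- W38 past the limit: 260 − 218 = 42 days.
- W38 past a rollover's nominal last visit: 260 − 211 = 49 days.
- With visit windows (±2 days in treatment, ±3 in follow-up), W38 can fall 45 days past Day 218 (W38 three days late) or 47 days (EoS also two days late).

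Under the schedule, W38 is required only for participants dosed from W27 onward. IMP continues until CRmin, so an on-schedule participant still without CR would normally meet that condition.

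**4. Size, by assumption.** The documents give no rollover rate. Let r be the share of an arm that does not roll over, and q the share of those who first reach CR after Day 218 with no prior intercurrent event.
- Rise in that arm's CR proportion = r × q.
- With r from 5% to 20% and q from 5% to 30%: 0.05 × 0.05 = 0.25 points up to 0.20 × 0.30 = 6 points.
- Bias in the treatment difference = (r × q in the efgartigimod arm) − (r × q in the placebo arm). With r = q = 10% in both arms it is 1.0 − 1.0 = 0. With r = 10% in both and q = 20% against 10% it is 2.0 − 1.0 = 1.0 point. At opposite corners of the assumed ranges it is 6 − 0.25 = 5.75 points, in either direction.

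**5. DC.** At the slowest recommended escalation (Protocol 6.8.1 and Table 3), a participant without DC spends 4 weeks on each of four dose steps and 3 weeks on the top step: 4 × 4 + 3 = 19 weeks. The treatment-failure criterion is thus reached well before Day 218, so a first DC after Day 218 is unlikely, though not excluded.

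**The case against.** The strongest reply is that little is at stake and the rule is pre-specified. Both proportions lie outside alpha control, were added in the SAP (6.1), and are not marked as topline tables. The flare endpoints in items 6 and 8 use follow-up openly. All of this stands and sets the priority low. It does not show that follow-up was intended for items 3 and 4, which, unlike items 6 and 8, are silent.

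The composite strategy also narrows the route. Qualifying immunosuppressants, immunoglobulin, anti-CD20 agents, plasma exchange or tetracyclines before the response make a participant a non-responder. For these endpoints so does any IV or IM corticosteroid (SAP 9.1.5), and so does stopping IMP for lack of efficacy. What remains is mainly a late CR on oral prednisone alone. This stands too.

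Some stronger readings are tempting, but the documents do not support them:
- *That follow-up belongs only to those who decline the extension.* SAP 3.1.1 also lists ineligibility and other reasons for not rolling over.
- *That a late CR is reached under usual care.* Protocol 6.6 mentions usual treatment for participants who withdraw or discontinue early. For the rest, off IMP is all that can be said.
- *That a Day 218 cut alone would make the proportions equal the time-to-event counts.* SAP 4.1.2 lets only the time-to-response endpoints use every measurement. Other endpoints use the assessment closest to target in each window, so a CR seen only at a non-selected visit would still be missed.
- *That a Day 218 limit removes all dependence on rollover.* Follow-up visits on or before Day 218 still count for early discontinuers who do not roll over (with ED by Day 169, both do: 169 + 49 = 218), as they do for time to CR.

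**Conclusion.** The point holds as a minor one. Under the SAP's own default, a first DC or CR after Day 218 can count for participants who do not roll over and, on schedule, for no one else. The extra time is up to 42 nominal days past Day 218 and 49 past a rollover's last visit. These figures assume visits on their nominal days.

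The practical effect is on CR; for DC it is probably negligible. A reader might take a within-arm inflation, such as the 0.25 to 6 points above, as the bias in the treatment effect. It is not: the shares are assumed, and only the between-arm difference in late responses biases the comparison. The documents allow neither its size nor its direction to be determined. Nor must the proportions and the time-to-event counts disagree through follow-up; that needs at least one first response after Day 218. The primary endpoint and the hierarchical tests are unaffected.

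**What to change.** In SAP 4.1.2.3, add to items 3 and 4: *DC/CR first achieved up to relative Day 218, using the same first-DC/first-CR date (all measurements) and ICE handling as the key secondary time-to-event endpoints.*

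The day limit removes the asymmetry after Day 218. The shared date and intercurrent-event rules make the proportions agree with the event counts for time to CR and time to DC. If responses in follow-up are meant to count, items 3 and 4 should say so, as items 6 and 8 do.

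The cost is one sentence and no new data. The reported proportions may be slightly lower.
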